## **20. Investigation of the utility of the prediction model**

From the validation sample, we will estimate its ability to rule-out the patients instead of the hospitalization. For that purpose, we will estimate the percentage of event-free patients at hospital discharge (no NSTEMI) among the ones with a predicted probability of event less than 0.3. We will also estimate the percentage of patients with a predicted probability of event less than 0.3.

From the validation sample, we will estimate its ability to rule-in the patients instead of the in-hospital evaluation at 0h by the percentage of patient with the event (NSTEMI) among the ones with a predicted probability of event higher than 0.65. We will also estimate the percentage of patients with a predicted probability of event higher than 0.65.

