## 7. Objectives and related endpoints (units and calculations used to derive outcomes)

An adjudication committee oversees the validation of the events considered in the following objectives and outcomes.

The primary objective is to determine the thresholds of the pre-hospital capillary and venous hs-cTnI that maximizes the Youden J index. The event to predict is the non ST-elevation acute coronary syndrome at hospital discharge (NSTEMI). The sensitivity is the proportion of patients with an hs-cTnI level higher or equal to the threshold among the patients with the syndrome. The specificity is the proportion of patients with an hs-cTnI level lower than the threshold among the patients without the syndrome. We will also determine the ROC (receiver operating characteristic) curves and the related areas under the curve (AUC) related to the two methods.

**Figure 1.** Decision tree for ruling-out ruling-in the patients with a suspicious myocardial infarction after their emergency admission.

The secondary objectives of the VALIDATE project are to study the discriminative capacities of the pre-hospital hs-cTnI measured by two different testing methods (capillary and venous whole blood), and to select the method with the best performances. For that purpose, we aim:

- To evaluate the most relevant hs-cTnI measurement between the capillary- and the venous-based methods by i) reporting the concordance between the pre-hospital hs-cTnI measured by the capillary and venous methods, and ii) comparing the related AUCs for discriminating patients with NSTEMI.
- To estimate and compare the discriminative performances of the two methods by considering the Major Adverse Cardiac Events (MACE) occurrence at 30 days (ROC curves, AUCs, and Youden J index). Note that a NSTEMI systematically implies an outcome of MACE at 30 days.

Depending on the results at this stage, the rest of the analyses will be performed according to the venous or the capillary method, depending on their discriminative performances. In case of an equivalence, we will choose the capillary method because of its feasibility in a real-life setting. We will further investigate its usefulness to improve the ruling-in and ruling-out process described in Figure 1. More precisely, we aim:

- To propose a pre-hospital predictive tool of the probability of NSTEMI at hospital discharge. The candidate predictors will be the available demographic, clinical data, and pre-hospital hs-cTnI level.

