## 8. Inclusion criteria

- Age  $\geq$  18 years.
- Chest pain for which a mobile emergency unit (HEMS) is dispatched for pre-hospital assessment.
- Chest pain evocative of AMI; medio- and retro-sternal, constrictive, radiating into the jaw, neck or left arm.
- Non-qualifying ECG or non-ST elevated ECG
- Non-opposition given by the patient after clear and fair information.

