## 9. Non-inclusion criteria

- Qualifying ECG with significant ST-segment elevation.
- Diagnosis of acute coronary syndrome has been ruled out by the HEMS physician.
- Patient care within 20 minutes of pain onset.
- Pregnant and/or breastfeeding women, women of childbearing age without contraception.
- Patients under guardianship, curatorship, or subordination.
- Patients benefiting from reinforced protection.

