## **16. Description of baseline patient characteristics**

The baseline characteristics will be summarized for the full cohort and according to the main and second outcomes, respectively: presence NSTEMI versus no NSTEMI and presence of MACE at 30 days versus no MACE at 30 days. The baseline is the time of the patient assessment by the HEMS.

The means, the standard deviations and the number of missing values will be presented for the following continuous variables:

- age (years)
- body mass index (kg/m^2)

The proportion of patients will be presented for the following categorial variables:

- Gender
- Risk factors of coronary artery disease (CAD):
  - HBP
  - Hypercholesterolemia
  - Diabetes mellitus
  - Family history of coronary artery disease
  - Active smoking
  - Past smoking (weaned > 5 years prior to recruitment)
- Cardiovascular history:

- Stented AMI
- Coronary by-pass
- Peripheral vascular disease
- Chronic kidney disease
- Stroke/ TIA
- Current medication:
  - ACE/ ARA2
  - Calcium inhibitors
  - Beta blockers
  - Anti platelet therapy
  - VKAs
  - Statins

We will also describe characteristics linked to the initial HEMS evaluation:

- Clinical presentation evocative of AMI on a 3-point scale (highly unlikely, moderately likely, highly likely)
- Delay between chest pain onset and HEMS evaluation ( $\leq 3$  hours versus  $> 3$  hours)
- HEMS ECG findings (normal, ST-segment depression, localized negative T-waves, left bundle branch block, other findings)

The frequency and percentage of patients in each category and the number of missing values will be reported for categorical variables: gender (male / female), risk factors (HBP, Hypercholesterolemia, Diabetes mellitus Family history of coronary artery disease, Active or past smoking), cardiovascular history and medication. For characteristics with multiple modalities, some may be merged in the case of small frequencies.

P-values will be reported with no correction for multiplicity. Categorical variables will be compared using a Chi-2 test (or Fisher exact test if the expected number of participants is less than 5), while continuous variables will be compared using a Student test (or Wilcoxon test if the minimum number of participants between the two groups is less than 30).

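### A patient enrolled without qualifying ST elevation but discharged with ST-elevation MI counts as event-free in the section 20 rule-out percentage

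*SAP*

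**What the plan says.** **Entry.** SAP section 8 admits "Non-qualifying ECG or non-ST elevated ECG", and section 9 keeps out "Qualifying ECG with significant ST-segment elevation". Both refer to the ECG at inclusion. Section 16 fixes that time point: "The baseline is the time of the patient assessment by the HEMS". The same section lists what may be seen on that tracing: "HEMS ECG findings (normal, ST-segment depression, localized negative T-waves, left bundle branch block, other findings".

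**Outcome.** Section 7 reads the outcome later: "The event to predict is the non ST-elevation acute coronary syndrome at hospital discharge (NSTEMI". Its control group for specificity is everyone else, namely those "lower than the threshold among the patients without the syndrome" and their counterparts above it. Section 19 fits the predictive tool to the same NSTEMI outcome.

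**Use.** For rule-out, section 20 says "we will estimate the percentage of event-free patients at hospital discharge (no NSTEMI", taken among patients with a predicted probability below 0.3. For rule-in it counts only NSTEMI among those above 0.65. Section 7 sets the targets: a negative predictive value of 99% in at least 5% of patients, and a positive predictive value of 65% in at least 10%.

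**Exclusions.** Section 12 removes patients for missing diagnosis data, and section 21 is complete-case. Neither mentions a discharge diagnosis of ST-elevation MI.

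**The concern.** Selection and outcome use different time points and different categories. An ECG that does not qualify at the HEMS assessment can evolve, so an enrolled patient can leave hospital with a diagnosis of ST-elevation MI. Under the SAP's labels that patient has no NSTEMI and so no event.

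For rule-out this is the unsafe direction: an infarction that the tool missed would be counted as a correct decision. The SAP itself supplies a route. Sections 15 and 19 note that troponin may still be rising in the first three hours and that this may add false negatives.

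The label also sits badly with the stated purpose. Section 7 justifies rule-in by faster treatment of MI in general, and its Figure 1 is captioned as a decision tree for suspected myocardial infarction.

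**Working it through.** **Where a discharge ST-elevation MI lands, by the written definitions**

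- Predicted probability below 0.3: in numerator and denominator of the rule-out percentage, so a success.
- Above 0.65: in the denominator of the rule-in percentage only, so a false positive.
- From 0.3 to 0.65: in neither percentage.
- In all three cases: a control for specificity and the Youden threshold (section 7), and a non-event in model fitting or, if in the validation third, in the AUC and calibration (section 19).

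**Inputs.** Section 10: sensitivity 95%, half-width 5%, prevalence 10%, 730 analysed. Section 19: one third for validation. Section 7: targets of 99% and 65%. The number of discharge ST-elevation MIs, k, is not in the SAP and is an assumption throughout.

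**The plan's own figure.** 1.96² × 0.95 × 0.05 / 0.05² = 72.99, so 73 cases; 73 / 0.10 = 730. Allowing for 10% loss gives 730 × 1.1 = 803 or 730 / 0.9 = 811, against 800 stated. The sample size reproduces closely enough and does not bear on this point. It gives 730 − 73 = 657 controls and about 730 / 3 = 243 validation patients.

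**Rule-out.** Let n patients be ruled out, with m missed NSTEMI and k ST-elevation MI among them. The plan reports (n − m)/n; the MI-free share is (n − m − k)/n. The plan shows the 99% target met while the MI-free share misses it exactly when m ≤ 0.01n < m + k.

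| n | m | k | Plan reports | MI-free |
|---|---|---|---|---|
| 12 (5% of 243) | 0 | 1 | 100% | 91.7% |
| 100 | 1 | 1 | 99.0% | 98.0% |
| 122 (50%) | 0 | 1 | 100% | 99.2% |
| 122 (50%) | 0 | 2 | 100% | 98.4% |
| 219 (90%) | 0 | 2 | 100% | 99.1% |
| 219 (90%) | 2 | 1 | 99.1% | 98.6% |

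The larger groups are the relevant ones. If the mean predicted probability is about 10%, the share at or above 0.3 cannot exceed 0.10 / 0.30 = 1/3, so at least 2/3 × 243 = 162 patients fall below the cut. At n = 162, one ST-elevation MI alone leaves 161/162 = 99.4%. One missed NSTEMI plus one ST-elevation MI gives a reported 99.4% against 160/162 = 98.8% MI-free.

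**Rule-in.** With 24 flagged (10% of 243) and 16 NSTEMI, the plan reports 16/24 = 66.7%. If k of the other eight have ST-elevation MI, the MI yield is 17/24 = 70.8% (k = 1), 18/24 = 75.0% (k = 2) or 19/24 = 79.2% (k = 3). The plan understates the tool here.

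**Specificity.** Let s be specificity among controls without ST-elevation MI. If all k such patients lie above the threshold, reported specificity falls by s × k/657. An assumed 1 to 3% of 730 is 7.3 to 21.9 patients. The fall is then at most 1.1 to 3.3 points (s = 100%), or 0.9 to 2.7 points at an illustrative s = 80%.

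**The case against.** **The protocol or an adjudication charter may settle this.** Section 7 has a committee validate events, and its rules are not shown. It might classify patients by the ECG at inclusion. That possibility stands and limits how surely one can predict what will happen. It does not cure the text, because a correctly validated ST-elevation MI is still not an NSTEMI and so is still event-free in section 20.

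**Such patients may be rare.** Section 9 removes significant ST elevation and also patients seen within 20 minutes of pain onset. No ST-elevation category appears among the section 16 ECG findings. Reading the inclusion criterion as admitting sub-threshold ST elevation is an inference, and bundle branch block or other findings do not show that ST-elevation MI is expected. All of this stands. The 1 to 3% used above is illustrative, and zero is compatible with the SAP.

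**The 30-day MACE analysis gives a broader outcome.** It does so for raw capillary and venous hs-cTnI (sections 7 and 18), but it is not applied to the tool or to section 20.

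**The worst cases cannot all occur together.** This is right. The full loss of specificity needs every such patient above the threshold, while the rule-out error needs a low predicted probability. One patient cannot be both a rule-out success and a rule-in false positive.

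**Conclusion.** Wrong as written, for the rule-out percentage. The definition counts a missed ST-elevation MI as a success, against a 99% target that one or two patients can decide. The conclusion about the definition needs no assumed rate; its numerical effect does, and the SAP supplies none.

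The effect on the target is conditional. It is hidden only when missed NSTEMI alone stay within 1% of those ruled out and the ST-elevation MIs carry the total past 1%. If missed NSTEMI already exceed 1%, the target fails either way. The rule-in error makes the tool look worse, so it gives no false reassurance. The effect on specificity is bounded above by the figures shown.

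A reader might infer more: that a sizeable share of the cohort will be mislabelled, that the tool will be wrongly declared safe, or that the primary event ought to become any MI. The SAP supports none of these. It gives no count. Changing the primary event would disturb the 10% prevalence and 73 cases behind the sample size, and would touch the separate question of whether unstable angina counts as a case.

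**What to change.** Keep NSTEMI as the primary event, and:

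1. In section 20, state that an adjudicated discharge diagnosis of ST-elevation MI is not event-free in the rule-out percentage.
2. Report beside that percentage the share free of 30-day MACE among those ruled out.
3. In the section 12 flowchart, report how many included patients were discharged with ST-elevation MI.
4. Add a sensitivity analysis of specificity, Youden threshold, AUC, negative and positive predictive values, with these patients counted as events and, separately, excluded.

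The cost is a few sentences and one extra set of tables. The SAP already plans for adjudicated diagnoses and 30-day MACE. The negative predictive value may look slightly less favourable.

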- To estimate its discriminative capacities by estimating the AUC and comparing its value with the one of the in-hospital HEART score estimated at 0h.
- To estimate its ability to rule-out the patients instead of the in-hospital evaluation at 0h for relieving emergency services, i.e., to achieve a negative predictive value equals to 99% (3) for at least 5% of the patients.
- To estimate its ability to rule-in the patients in the cardiology department instead of the in-hospital evaluation at 0h for reducing the time to treatment of the MI, i.e., to achieve a positive predictive value equals to 65.0% (Figure 1) for at least 10% of the patients.
- To evaluate its increase of capacities for discriminating patients with NSTEMI by considering additionally the venous troponin measured in hospital (difference in the AUC).

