## **10. Sample size**

For the primary objective, we expect a sensitivity of 95%. We aim to include 73 patients for a maximum length of the 95% confidence interval equals 10% (+/-5%). Assuming a NSTEMI prevalence of 10%, 730 patients must be analyzed to achieve this precision. By anticipating a 10% rate of non-exploitable data (missing value, lost to follow-up, etc.), 800 inclusions are necessary.

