## **13. Level of statistical significance (p-values, confidence intervals, one- or two-sided)**

Statistical significances will be achieved for p-values lower the 5% by using two-sided alternative hypotheses and two-sided 95% confidence intervals. The 95%CI will be estimated by non-parametric bootstrap.

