## **19. Proposition and validation of a predictive tool for pre-hospital rule-out and rule-in**

The cohort will be divided into two parts: two thirds for learning and one third for validation. The description of the two samples will be performed with the same baseline variables listed in the section 16. No p-value will be computed because of the random allocation of the patients. Instead, standardized mean differences will be estimated to evaluate the comparability of the two samples.

From the learning sample, a logistic model will be estimated with LASSO penalization to select the subset of predictors among the following list of candidates: age, gender, body mass index, active smoking, stented heart disease, bypassed heart disease, compatible clinical history, delay after onset of pain lower than 3h; normal ECG evaluated by the HEMS, and the following risk factors: hypertension, diabetes, hypercholesterolemia, family history and hs-cTnI. The outcome will be the diagnosis of NSTEMI. We will perform a 20-fold deviance-based cross-validation to choose the best tuning parameter.

A particular attention will be paid to the interaction between hs-cTnI and the delay after onset of chest pain because the level of troponin may continue to grow up to three hours after the chest pain. This may lead to increase the proportion of false negatives.

From the validation sample, we will estimate its discriminative capacities by the ROC curve and the related AUC. Its goodness-of-fit will be evaluated by a calibration plot of the observed probabilities against the mean predicted probabilities for five subgroups of equal size. The corresponding Hosmer and Lemeshow statistic will be estimated.

Always from the validation sample, we will compute the in-hospital HEART score at 0h, the related ROC curve and AUC, and its difference with the pre-hospital predictive model.

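### The fixed cut-offs of 0.3 and 0.65 in SAP section 20 do not answer the NPV and PPV targets in section 7; the gap is large for rule-out and conditional for rule-in

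*SAP*

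**What the plan says.** Section 7 sets two joint targets for the tool. For rule-out it is "to achieve a negative predictive value equals to 99% (3) for at least 5% of the patients". For rule-in it is "to achieve a positive predictive value equals to 65.0% (Figure 1) for at least 10% of the patients".

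Section 20 is the analysis of these objectives, in the validation sample. For rule-out it takes the proportion without the event ("no NSTEMI) among the ones with a predicted probability of event less than 0.3") and the share of patients in that group. For rule-in it takes the proportion with NSTEMI "among the ones with a predicted probability of event higher than 0.65", again with the share. It does not restate the 99%, 5% or 10%, does not look for a cut-off that reaches a target, and gives no reason for 0.3.

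Section 19 splits the cohort into "two thirds for learning and one third for validation" and plans a LASSO logistic model: "We will perform a 20-fold deviance-based cross-validation to choose the best tuning parameter".

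**The concern.** A target on a group's predictive value is not the same as a cut-off on an individual's predicted risk. Section 7 asks whether a small group at very low risk can be found. Section 20 measures a large mixed group that runs up to a 30% risk of NSTEMI. For rule-in, section 20 uses the 65% PPV target itself as the individual-risk cut-off. In a calibrated model, PPV above that point exceeds 65%, and the group is smaller than the one that just meets the target.

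Section 20 has no pass/fail rule, so no formal test goes wrong. What is at stake is that a tool able to meet the section 7 target would be reported with a figure that appears to miss it. If other cut-offs were then chosen on the validation data, the split-sample validation would be lost.

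**Working it through.** **Inputs from the SAP.** NSTEMI prevalence 10% and 730 analysed patients (section 10: "Assuming a NSTEMI prevalence of 10%, 730 patients must be analyzed to achieve this precision"); one third for validation (section 19); targets from section 7; cut-offs from section 20. The section 10 figures reproduce: 1.96² × 0.95 × 0.05 / 0.05² = 72.99, so 73 cases, and 73 / 0.10 = 730. The validation third then has 730 / 3 ≈ 243 patients and about 24 NSTEMI; the learning part has about 487 patients.

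**Assumptions.** The SAP gives neither the tool's AUC nor the shape of its risk distribution, so both are varied.

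**Step 1: bound without a model shape (10% prevalence).**
- Calling everyone negative already gives NPV 90%.
- In a calibrated model, the share with risk of 0.3 or more is at most 0.10 / 0.3 = one third. At least two thirds therefore lie below 0.3.
- Let s be the share below 0.3. If NPV there is 99%, then 0.99s ≤ 0.90, so s ≤ 0.909. The fraction of NSTEMI in that group is 0.01s / 0.10 ≤ 9.1%. So at least 91% of all NSTEMI must have a predicted risk of 0.3 or more.

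**Step 2: size of the rule-out gap.** Scores are N(0,1) in non-events and N(d,1) in events, with d = √2 · Φ⁻¹(AUC) and calibrated risk. A risk cut-off c lies at x = d/2 + [logit(c) − logit(0.10)] / d. For AUC 0.85: d = 1.466 and x = 0.733 + 1.350 / 1.466 = 1.654. Non-events below: Φ(1.654) = 0.951. Events below: Φ(0.188) = 0.575. Share = 0.9 × 0.951 + 0.1 × 0.575 = 0.913. NPV = 0.856 / 0.913 = 93.7%.

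| AUC | Share with p<0.3 | NPV at p<0.3 | NSTEMI with p<0.3 | Cut-off where NPV is 99% | Share below it |
|---|---|---|---|---|---|
| 0.80 | 93% | 92.4% | 70.5% | 0.017 | 15% |
| 0.85 | 91% | 93.7% | 57.5% | 0.021 | 32% |
| 0.90 | 90% | 95.2% | 44% | 0.029 | 52% |
| 0.95 | 89% | 96.9% | 28% | 0.054 | 74% |

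AUC needed for each statement:

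| Prevalence | NPV 99% at p<0.3 | NPV 99% in 5% of patients |
|---|---|---|
| 5% | 0.986 | 0.690 |
| 10% | 0.993 | 0.755 |
| 20% | 0.996 | 0.815 |
| 30% | 0.998 | 0.850 |

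With an event SD 1.5 times the non-event SD (10% prevalence) the two values are 0.992 and 0.893: narrower, but still apart. In 20,000 simulated validation samples of 243, the observed NPV at p<0.3 reached 99% in 0.01%, 0.13% and 3.2% of samples at AUC 0.85, 0.90 and 0.95.

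**Step 3: rule-in, same equal-variance model.** At 10% prevalence, PPV 65% in 10% of patients is attainable only from AUC 0.936; below that, the fixed and the target-based cut-off give the same answer. At AUC 0.95, p>0.65 holds 5.6% of patients with PPV 86%, whereas the group with PPV 65% holds 11.3%. At higher prevalences the answers differ only within a band of AUC: 0.866 to 0.955 (prevalence 15%), 0.813 to 0.898 (20%), 0.729 to 0.797 (30%). At 5% prevalence the target cannot be met at all, since the top 10% of patients could have PPV of at most 0.05 / 0.10 = 50%.

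**Step 4: which replacement rule works.** 200 learning samples of 487 were simulated per scenario, with 14 candidate predictors and LASSO tuned by 20-fold cross-validation, at AUC 0.83 and 0.91. Share of runs in which the true NPV below the chosen cut-off was at least 99%:

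| Rule | AUC 0.83 | AUC 0.91 |
|---|---|---|
| p<0.3 | 0% | 0% |
| Observed NPV, in-sample predictions | 15% | 23% |
| Observed NPV, out-of-fold predictions | 28% | 48% |
| Mean out-of-fold predicted risk ≤1% | 66% | 65% |

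The last rule excluded a median of 16% and 51% of patients.

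**The case against.** Five points can be made for the plan.

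- **The calibration plot in section 19 shows part of the answer.** It uses five equal groups, and the lowest fifth (about 49 of 243 patients) shows NPV in 20% of patients. In the same binormal model that fifth reaches NPV 99% from AUC 0.818 at 10% prevalence. This stands as far as it goes, but the plot is planned as a goodness-of-fit check, not as the rule-out analysis, and cannot isolate a 5% group.
- **The fixed cut-offs can show success.** If NPV below 0.3 reached 99%, the rule-out target would be met, because that group is so large. Likewise PPV of at least 65% in at least 10% of patients above 0.65 would meet the rule-in target. True; but a figure below 99%, or a share below 10%, would not show that the target is missed.
- **The AUC limits depend on shape.** A two-level score with sensitivity 95%, an assumed specificity of 80% and prevalence 10% gives positives a risk of 0.095 / 0.275 = 0.345 and NPV 0.72 / 0.725 = 99.3%, at AUC 0.875. So the AUC limits above belong to the models computed. The shape is extreme for a model with 14 candidates, and the bound in step 1 still holds.
- **The objectives are secondary and will be imprecise in any case.** Both are correct. Neither makes the planned figures answer the stated question.
- **0.3 may have a reason outside the text reviewed, or be a misprint.** The content of Figure 1 was not available, so a rationale cannot be excluded. A value of 0.03 would lie within the 0.017 to 0.054 range found above, but the SAP does not say so. Either way, the two sections have to be reconciled.

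**Conclusion.** The concern holds. The mismatch between sections 7 and 20 is in the text and needs no model. For rule-out it is large: at 10% prevalence in the equal-variance model, any tool with AUC between about 0.755 and 0.993 could meet the section 7 target while section 20 reports an NPV below 99%. For rule-in it is conditional: the PPV part would be met, only the share is understated, and at 10% prevalence this matters only from AUC 0.936.

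The AUC figures rest on assumed calibration and score shape; the two-thirds and 91% bounds rest on calibration and the SAP's 10% prevalence alone. The primary threshold and the sample size are not affected. The case for correcting the SAP rests on the rule-out half, and the change should be made before the validation sample is analysed.

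**What to change.** Keep the section 7 targets and replace the fixed cut-offs in section 20, for example:

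> In the learning sample, using the out-of-fold predictions of the 20-fold cross-validation, the rule-out cut-off is the largest predicted risk below which the mean out-of-fold predicted risk is at most 1%. The rule-in cut-off is the smallest predicted risk above which the mean out-of-fold predicted risk is at least 65%. Both are locked before the validation sample is analysed. In the validation sample we report NPV and the share ruled out (against 99% and 5%), and PPV and the share ruled in (against 65% and 10%), with exact 95% confidence intervals.

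If 0.3 and 0.65 serve another purpose, state it and report them in addition.

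Use exact (Clopper-Pearson) intervals here in place of the general rule in section 13 ("The 95%CI will be estimated by non-parametric bootstrap"). A rule-out group with no NSTEMI gives a bootstrap interval of 100% to 100%. At a true NPV of 99% this happens with probability 0.99^38 = 68% in a group of 38 patients and 0.99^124 = 29% in a group of 124 (roughly the median shares of 16% and 51% applied to 243).

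**Cost.** SAP wording and a few lines of code; no new data, since the out-of-fold predictions come from the cross-validation already planned. The SAP should state the limits. The cut-offs are data-derived and rely on calibration, and in the simulations the rule reached a true NPV of 99% in about two thirds of runs. Precision is low: with no NSTEMI in the rule-out group, the exact lower limit 0.025^(1/n) is 73.5% for 12 patients (5% of 243), 90.7% for 38 and 97.1% for 124. A lower limit of 99% needs 368 event-free patients, more than the whole validation sample, so the NPV target can be judged there on the point estimate only.
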